### **Intervention (See appendix C)**

For the SA intervention, participants will be asked to rank 11 items (artistic skills, athletics, business/money, creativity, independence, music, politics, relationships with friends and family, religious values, sense of humor, spontaneity) from most important to least important (Creswell et al., 2013; Havranek et al., 2012). They will then be asked to write about the item that is most important to them and why it may be important to them. The control group will rank the same list and be asked to will write about the 9th ranked item and why it might be important to someone else. The control condition is consistent with the control used in other SA intervention studies.

Immediately after the intervention or control condition, participants will complete a 2 minute survey that consists of the short version of the Stat-Trait Anxiety Inventory (STAI). This measurement entails 6 questions to assess the client's current anxiety. The purpose of the STAI is to control for anxiety, to identify if those who are more anxious are more effected by the SA intervention. The intervention and STAI should take about 10-15 minutes together. At the end of the intervention there will be a detachable page asking for the client's email address to send them with the post-intervention survey and a reminder to complete it. This document will be immediately separated from the study material by the scheduling coordinator.

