A meta-analysis of SA and responses to health messages assessing both intentions and behaviors in 16 studies found that aggregate effect sizes for health intentions and health behaviors were statistically significant but low at  $d = 0.26$  and  $d = 0.27$  respectively (Sweeney & Moyer, 2015). Behaviors and health intentions in this study were both negative (e.g. reducing caffeine intake or alcohol consumption) and positive (e.g. increasing sunscreen or condom use). It should be noted that 12 of the 16 studies reviewed used student samples where the threat was either far off (e.g. sunscreen use and skin cancer) or not personalized so the perceived threat of the message may have been low. In the proposed study the risk for HBOC cancer is personalized by family history or personal early onset cancer and the threat of cancer is either immediate or high. Since stress and heightened risk appraisals appear to moderate the effect of SA as an intervention, we would expect the effect of SA in this population to be higher than those in the meta-analysis.

Other studies have addressed SA and client engagement in a medical encounter. A randomized controlled trial of SA in African American clients with hypertension found that the SA treatment group requested and provided more information about their medical condition from their primary care provider in a medical encounter. Additionally, in the SA group, the patient-provider communication was characterized as being more interested, friendly, responsive, interactive, and respectful (Havranek et al., 2012). Since SA is postulated to increase message acceptance and to decrease motivation to avoid the threat, it is consistent that clients may attend to the threatening message more carefully and remember information about HBOC more accurately (Harris & Epton, 2009).

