Appendix C) (Creswell et al., 2013; Havranek et al., 2012). They will then be asked to write about the item that is most important to them and why it may be important to them. The control group will rank the same list and be asked to write about the 9th ranked item and why it might be important to someone else. The control condition is consistent with the control used in other SA intervention studies. The 9th ranked item is chosen to inhibit a reverse effect where participants feel affirmed because they do not value something that is aversive to them. Both the intervention and control group will receive a 6-question survey of state anxiety along with the writing prompt, which will be used as a control measure.

Potential participants will be identified through the patient schedule and will be contacted by the student assistant investigator (AI), [name], about one week prior to their appointment to invite them to participate in the study and obtain verbal informed consent. Participants will be recommended to arrive 15 minutes prior to their scheduled appointment. When clients arrive at the HBOC clinic, the front desk staff will give client participants the SA or control intervention based on random assignment. The affirmation intervention or control condition will be completed directly before the regularly scheduled appointment.

Genetic counselors will be blinded to the study condition of their clients, although clients might choose to discuss the content of the intervention survey with the counselor. Counseling sessions will otherwise proceed according to protocol for the clinic. Clients will receive a paper survey as they leave the appointment regarding their demographic information (age, sex, education, race, ethnicity, cancer status) experience in the study, decision self-efficacy, empowerment, genetic knowledge, intentions to talk with family, information seeking, and intentions to pursue genetic testing if it was offered. They will be given the option to fill out the paper version or to access an electronic version online. Hard copy surveys will be returned to the front desk or by mail to the AI. Electronic versions will be sent to an email address provided by the client. A week after their appointment, all clients will receive an electronic reminder notification to complete the questionnaire. Upon completion of the online survey or paper questionnaire participants will be mailed a \$15 gift card.

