## **7.0 Description of study statistical considerations and/or analytic plan:**

*Aims have been copied here for ease of interpretation.*

Aim 1: To assess the preliminary impact of a novel SA intervention on outcomes that may be targeted in future studies, by assessing differences in the following between a SA intervention and unaffirmed standard SA intervention control group of HBOC genetic counseling clients:

- a. Intentions to talk with family, test uptake
- b. Empowerment, decision self-efficacy
- c. HBOC knowledge

The primary goal of analysis of aim 1 is to identify which outcomes would be most appropriate for follow up studies and the necessary sample size for adequate statistical power.

For decision efficacy, the scores on the Decision Self-Efficacy Scale (See section 2 of client survey, Appendix D) will be compared between groups using linear regression controlling for education, race, anxiety score, and effectiveness of intervention (based on last question on intervention Appendix C). Intention to talk with family, genetic testing uptake, and information seeking will be measured similarly using linear regression.

Client empowerment will be analyzed by using the GCOS-24 a 24-item likert scale completed by clients and parallel scale by genetic counselors (See section 3 of client survey of appendix D and appendix F). Both scales will be compared between groups using linear regression controlling for education, race, anxiety score, and effectiveness of intervention (based on last question on survey). Discrepancies between counselor and client surveys will be analyzed using dyadic analyses. For this analysis, we will assess the correlation between paired client and genetic counselor GCOS-24 for the compete survey and for the individual questions.

HBOC knowledge will be analyzed between groups using linear regression testing the knowledge scale (See section 4 of client survey, Appendix D) and controlling for education, race, anxiety score, and effectiveness of intervention.

Effect sizes and standard deviations for each outcome will be identified, and an estimated sample size for a fully powered study will be estimated based on power calculations.

Aim 2: To describe genetic counselors' (GCs) and clients' response to a novel, client-based SA intervention, including perceived impact, barriers, and facilitators to implementing such an intervention on a wider scale

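### The STAI is given an effect-modification purpose that no analysis in section 7.0 serves, and it is completed after the randomised writing task

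*Combined protocol and SAP*

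**What the plan says.** Three parts of the document describe what the STAI is for.

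- **Section 5.6, Intervention (See appendix C).** Besides controlling for anxiety, the measure is there "to identify if those who are more anxious are more effected by the SA intervention". The same paragraph has clients complete the six items directly after the self-affirmation (SA) or control writing task.
- **Section 5.0.** The six-item survey is handed out with the writing prompt, "which will be used as a control measure". An earlier paragraph says it should account for variability in indication. Neither place mentions moderation.
- **Section 7.0, Aim 1.** Decision Self-Efficacy Scale scores "will be compared between groups using linear regression controlling for education, race, anxiety score, and effectiveness of intervention". For the client and counselor GCOS-24, "Both scales will be compared between groups using linear regression controlling for education, race, anxiety score, and effectiveness of intervention". The knowledge scale is analysed "controlling for education, race, anxiety score, and effectiveness of intervention". For the rest, "Intention to talk with family, genetic testing uptake, and information seeking will be measured similarly using linear regression".

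No interaction term, anxiety subgroup or other moderation analysis appears anywhere in section 7.0, and none of the three aims names one.

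**The concern.** Whether more anxious clients are more affected by SA is a question about how the arm difference changes with anxiety. A regression that only adjusts for anxiety assumes one arm difference at every anxiety level. The plan therefore states a purpose for an instrument and then specifies models that cannot serve it.

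The timing adds a second difficulty. A moderator should describe the client before assignment can act on her. A score read after the randomised task may differ between arms because of the task, and being more anxious could then be partly a result of assignment. Adding the interaction to the data as now collected would not give a clean answer.

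What is at stake is limited but practical. A stated question will go unanswered, or it will be answered after the fact by an unplanned analysis on a post-task score.

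**Working it through.** **1. The plan's own sample-size figure.** Section 6.1 gives 296 participants for d = 0.35 and alpha 0.05, with 0.85 read as power. A two-sided two-sample t-test gives 147.55, so 148 per arm and 2 × 148 = 296. The figure reproduces. It concerns the overall arm difference only; the document gives no figure for an interaction.

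**2. What the planned model can estimate.** Leaving out the other covariates, the planned model is

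Y = b0 + b1·arm + b2·anxiety + error.

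The question in section 5.6 concerns b3 in

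Y = b0 + b1·arm + b2·anxiety + b3·arm·anxiety + error.

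Suppose allocation is 1:1 and anxiety is standardised and unrelated to arm. If the second model is true and the first is fitted, the arm coefficient still estimates b1, the effect at average anxiety, and the anxiety coefficient estimates b2 + b3/2. Nothing in the fitted model isolates b3. A simulation agrees (N = 70, b1 = 0.35, b2 = 0, unit residual SD, 3,000 runs per case):

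| True b3 per SD of anxiety | Mean arm coefficient | Mean anxiety coefficient |
|---|---|---|
| 0 | 0.348 | about 0 |
| 0.35 | 0.354 | 0.18 |
| 0.50 | 0.347 | 0.25 |

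The arm coefficient is the same in all three cases. The anxiety coefficient moves, but it would move in the same way if anxiety simply predicted the outcome in both arms.

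**3. Precision if the interaction is added.** With 1:1 arms and a standardised moderator, the product of centred arm and anxiety has SD 0.5 × 1. Hence SE(b3) = σ/(√n × 0.5) = 2/√n in units of σ, the residual SD, taken here as roughly the outcome SD. The relevant n is the number of clients with a usable pre-task score. Section 5.0 plans 70 clients. Section 6.1 says recruitment has begun, at about 8 a month instead of 17, but not how many are enrolled. The values 35 and 20 are therefore assumptions.

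| n with pre-task score | SE = 2/√n | 95% CI half-width = 1.96 × SE |
|---|---|---|
| 70 | 2/8.367 = 0.239 | ±0.47 |
| 35 | 2/5.916 = 0.338 | ±0.66 |
| 20 | 2/4.472 = 0.447 | ±0.88 |

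For an assumed interaction of 0.35 per SD at n = 70, power is Φ(0.35/0.239 − 1.96) = Φ(−0.50), about 31% (28% in the simulation). The further covariates in section 7.0, and code words that cannot be matched (section 10.3), would widen these intervals somewhat.

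**4. Timing.** Section 5.6 states the order: task, then STAI. Section 5.0 places the STAI before the appointment and in the same packet as the prompt. Both statements fit the order in section 5.6, so the score is a post-randomisation measure.

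**The case against.** The strongest reply is that this is one clause, not an aim. Section 5.0 gives the STAI a control role only. Section 7.0 says the Aim 1 analysis is meant to find suitable outcomes and the sample size for a later study, and its models serve that goal. Rewording section 5.6 would remove the mismatch at no cost. This stands: it keeps the point modest, and deletion is an acceptable remedy.

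A second reply is that the interaction would be too imprecise to settle anything. It would be imprecise, since even ±0.47 exceeds the main effects of 0.26 and 0.27 cited in section 3.0. But section 3.0 also says significance is not expected and that the study is to supply effect sizes and intervals. An exploratory estimate fits that purpose; a significance claim would not.

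A third reply is that reordering the packet during recruitment leaves the anxiety score pre-task for some clients and post-task for others in every main model. This is correct, and the fix needs a rule for it.

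Some stronger readings are tempting but not supported:

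- *That the pilot should inform whether the next trial selects or stratifies anxious clients.* The document mentions no such decision.
- *That the argument in section 3.0 for a larger effect here would be tested by this term.* That argument, "Since stress and heightened risk appraisals appear to moderate the effect of SA as an intervention", compares populations: mostly student samples facing distant or impersonal threats against clients with personalised, immediate or high risk. A state-anxiety interaction within this clinic sample would not test it. The student study cited there, with a stress-by-SA interaction at p = .041, used chronic stress; it makes the question reasonable but does not predict the answer.
- *That section 9.0 says the writing task itself raises anxiety.* It ties possible anxiety to openness to a threatening message. The timing concern rests on the general principle that a score taken after assignment may be affected by it.

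**Conclusion.** The mismatch is real and can be read directly from the text: section 5.6 poses an effect-modification question, and section 7.0 contains no estimate that addresses it. The score as now timed is also not a clean moderator, because it follows the randomised task. The document does not show that assignment changes the score, only that the order allows it.

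The weight is modest. No numbered aim depends on this question, and the omission of an interaction does not by itself undermine the estimates planned for Aim 1. The ±0.47 half-width is a best case that requires 70 pre-task scores. With recruitment under way, a reordered packet cannot deliver that many unless clients are recruited beyond the planned 70. The precision figures assume 1:1 allocation among the clients counted, a linear interaction and complete data.

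**What to change.** **If the question is kept:**

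1. In section 7.0, add an arm-by-anxiety interaction for each scale outcome. Label it exploratory and report it as an estimate with 95% CI and no significance claim.
2. For clients still to be enrolled, place the six STAI items before the ranking and writing task, and align sections 5.0 and 5.6 with that order.
3. Record which packet order each client received. Base the interaction on pre-task scores only. Report clients from the present order separately, described as post-task anxiety, and do not read their result as modification by pre-task anxiety.
4. Do not pool pre-task and post-task scores as one covariate in the main models. One workable rule is to report the main arm comparison without the post-task score.
5. State precision using the actual number with pre-task scores, through SE of about 2/√n.

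**If the question is not kept:** delete the moderation purpose from section 5.6, so that the STAI has the control role described in section 5.0.

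The cost is one reordered page, one model term per scale outcome and one recorded variable for packet order. There are two drawbacks. Only later clients contribute to the interaction. Answering anxiety items first may also prime clients; this would apply to both arms alike, but early and late enrollees would then have had somewhat different packets. Deletion costs one edited sentence.

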### **Client post-intervention survey (Appendix D)**

Client surveys will consist of questions on each category of outcome (information seeking, test uptake, empowerment, intention to talk with family, decision self-efficacy, and HBOC knowledge) as well as response to and acceptance of the SA measure. The survey will be offered online and in person. It should take less than 15 min for participants to complete. At the end the hard copy post-intervention there will be a page for clients to enter their mailing address to receive the gift card, this page will be immediately separated from the other study materials by the scheduling coordinator. The online survey will have a separate link for clients to enter their mailing address.

**Decision self-efficacy.** To measure decision self-efficacy in decisions regarding genetic testing for HBOC and we will use the Decision Self-Efficacy Scale (O'Connor, 1995). This scale focuses on the decision process and interactions with the medical professional so it gives insight into both decisional efficacy and clients' engagement with the clinician.

**Test uptake.** For this section we will ask two questions to test uptake; "Did your counselor offer you genetic testing in your counseling appointment?" (yes/no) and "If yes, do you plan to have genetic testing?" (yes/no).

**Intention to talk with family.** Intention to talk with family will be measured using two questions. The first is a question asking clients to select the categorical description of the family group they are most likely to share information with from a list of options, such as "I plan to talk to only a few people who are closest to me." The second question will state "How likely are you to share results with the relatives you selected?" will be rated on a 1-7 likert scale labeled "extremely likely to extremely unlikely."

**Empowerment.** Empowerment will be assessed using the valid and reliable Genetic Counseling Outcomes Survey (GCOS-24) (McAllister et al, 2011). The GCOS-24 is a 24 item instrument that was designed to measure positive outcomes of genetic counseling. Empowerment was conceptualized to include decisional control, cognitive control, behavioral control, emotional regulation, and hope. The scale has seven dimensions, which exist under a single higher order construct.

**Client Knowledge.** Client knowledge will be measured using modified questions based on the National Center for Human Genome Research Knowledge scale and genome sequencing knowledge items from Kaphingst and colleagues study of informed consent on genome sequencing knowledge (Kaphingst et al., 2012; Scherr, Christie, & Vadaparampil, 2015). These questions focus on the main knowledge concepts rather than specific details since counseling sessions may differ depending on patient's indication for genetic counseling.

**Response to SA measure.** This section will ask both open ended and yes/no questions regarding clients' acceptance of and response to the intervention or control. There is also a question asking if and how clients thought that the measure affected their counseling session to identify any overt interference of the measure with their session.

### **Counselor after visit survey (Appendix E)**

The counselor after visit survey consists of a counselor version of the Genetic Counseling Outcome Scale (GCOS-24). This scale was modified from the original GCOS-24 for use by counselors and parallels the client version. This measure consists of 24 likert scale questions that assess counselor's perceptions of the client's empowerment. It should take 3-5 minutes for the counselors to complete after each session.

### **Counselor post-study survey (Appendix F)**

The counselor post-intervention surveys will include four yes/no questions with related open-ended response questions regarding the intervention. It also includes one likert scaled question and a place for any other thoughts on the study. This survey should take about 10 minutes to complete.

## **6.0 Description of study population**

#### 6.1 Estimated number of participants, enrollment ceiling, and anticipated enrollment by year.

The client participants will be female patients being seen at the high-risk breast and ovarian cancer clinic at St. Luke's Health System and Medstar Washington Hospital Center, for their initial appointment for genetic counseling for HBOC. Participant selection will be indiscriminant of if they have cancer or if they have already had genetic testing through another provider. Participants must be at least 18 years of age. For a fully powered study of the effect of self-affirmation on genetic counseling outcomes, we estimate that we would need 296 participants to identify a small to medium effect (Cohen's  $d = 0.35$ ) with beta being 0.85 and alpha being 0.05. This Cohen's  $d$  is based on other SA interventions in the education and emerging medical literature. For this feasibility study we seek to recruit 70 client participants and 4 genetic counselor participants. We chose this number for several reasons. The genetic counselors at St. Luke's Health System see about 40 new patients a month. Over the 4 months of data collection there will be 180 appointments. We believe that getting 70 of these clients to consent is an achievable estimation. Additionally, feasibility studies typically range from 30-50 participants to estimate attrition and confidence intervals. The enrolment ceiling is 180 participants. Genetic counselor participants two genetic counselors at the St. Luke's health system HBOC clinic. Participants will be enrolled by February of 2018. To this point, we have been recruiting about 8 patients a month instead of expected 17 through St. Luke's Health System. To our knowledge, this is because the counselors are seeing more colorectal and other cancer patients than expected instead of HBOC patients and we have been able to reach less patients for consent. About half decline to be contacted and 1/3 cannot be reached by the AI for consent. For this reason, we are adding the Medstar Washington Hospital Center site and extending the recruitment window. Genetic counselor participants are two genetic counselors employed in the HBOC genetic counseling clinic at St. Luke's Hospital and two genetic counselors who see HBOC patients at Medstar Washington Hospital Center.

#### 6.2 Description and justification of clinical inclusion/exclusion criteria.

Participants must be female, at least 18 years old, and have an initial appointment for genetic counseling for HBOC risk at St. Luke's health system or Medstar Washington Hospital Center. Participants will not be discriminated against for race, ethnicity, or income. Participants must be able to read and write in English to participate. Non-English speakers and illiterate subjects will be excluded. The intervention and measures have not been validated in other languages and therefore we are limiting the language to English. We will assess feasibility before validating the measures and intervention in another language. Since this is a feasibility study we will not have sufficient power to validate the measures. Follow-up studies should include more diverse populations. Clients who are unable to provide consent will be excluded. Pregnant women will be included. This is appropriate under 45 CFR 46.204 because this is minimal risk research necessary to develop important knowledge that cannot be obtained by other means. It will be the case that: 1) no inducements, monetary or otherwise, will be offered to terminate a pregnancy; 2) individuals engaged in the research will have no part in any decisions as to the timing, method, or procedures used to terminate a pregnancy; and 3) individuals engaged in the research will have no part in determining the viability of a neonate.

The study will be limited to women because the majority of clients at a hereditary breast and ovarian cancer clinic are women and we do not estimate that there will be enough male clients to independently analyze their responses.

Genetic counselor participants must be certified genetic counselors and see clients with an indication for HBOC related genetic counseling.

